7 STUDY SCHEDULE

7.1 Screening

Project staff will collaborate with LBHC and the CAB at Crow and the WIC clinic and Head Start staff at Hopi to identify pregnant women who meet inclusion criteria. Written information explaining the study purpose will be disseminated to all potential participants. Participants will be given an orientation to the project, including the intervention schedule and study risks and benefits. No medical record screening is required for participation.

Screening Visit (Day -28 to -1)

Confirm that potential participants are:

- 18 years or older
- Pregnant (3-7 months)
- American Indian or giving birth to an AI child (as reported by the mother)
- Able and willing to participate until the child is age 3
- Living within approximately 100 miles of the Crow or Hopi Nations
- Not enrolled in other community health interventions that incorporate oral health intervention, e.g., Family Spirit Program at Hopi
- Not a member of the Northern Cheyenne Tribe
- Not living on the Navajo Nation and a not a member of the Navajo Tribe

Following confirmation of eligibility participants may be consented into the study. At this point the formal coverage of the consent form will occur and study staff will obtain and document consent from potential participants. Following completion of informed consent (documented in REDCap) the participant will be randomized by NAU staff to either the Healthy Lifestyle or Oral Health arm. At this point participants are officially enrolled in the study and will be referred to a CHR to schedule the first study visit. A small subset of demographic questions (~20 items) will be assessed at the consent visit.

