12.2 Sample Size Considerations

A Cochrane meta-analytic review⁹ estimated that fluoride varnish reduces the prevalence of decayed, missing and filled first teeth surfaces (dmfs) by 37%. An Indian Health Services survey reported a mean dmfs in 2-year olds of 10.05 (standard deviation [SD]=16.27).¹⁴ A 37% reduction from this low base rate would require prohibitively large samples from these communities. To increase sensitivity and efficiency we will follow our sample from a minimum of 2 years and some children to a maximum of 3 years of age. Recent data from 3-year olds on the Navajo Nation showed a mean dmfs of 18.2 (SD=19.4). Therefore, for sample size calculations, we estimate values halfway between ages 2 and 3, i.e., mean dmfs=14 (SD=17.25). Using Stata 15.1 (StataCorp, College Station, TX) with power = 0.80, alpha = 0.05 (two tailed) for an independent *t*-test a sample of 352 is necessary to detect a 37% reduction in caries experience (dmfs of 14 vs 8.8; SD=17.25). To cover the estimated 19% attrition rate reported in the Cochrane review would require 434 participants. This is the theoretical maximum sample size necessary in this context. However, sample size estimates are highly sensitive to the estimated variability of dmfs measurements. A 35% reduction in the standard deviation (SD=11.2) for the same effect size would require only 150 participants for power = 0.80 (N=185 to cover attrition). Prior studies in AI groups have not evaluated fluoride varnish application in combination with prenatal maternal intervention using MI techniques and care coordination. This novel and intensive treatment combination should produce a larger effect than varnish alone and also reduce extreme caries experience, i.e., reduce dmfs variability. Our statistical sensitivity is also enhanced by following early enrollees up to an average expected age of ~ 2.5 years. Our recruitment timeline targets enrollment of 350 pregnant women across both sites. With 19% attrition we would retain an effective sample size of 283.5. To be

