conservative we round down to an even number of 282 (141 per group) which provides power of 0.71 for a 2-tailed test with alpha .05 and a 37% treatment group difference in dmfs. This sample size achieves power = 0.97 under the smaller standard deviation assumption. Current standards of care recommend FV application for all children at high risk for caries. Study staff will therefore apply FV to children in the Healthy Lifestyle group at 12 and 24 months of age. This will potentially dilute between groups caries differences but is a necessary accommodation given the high caries burden in AI communities.

We feel this is a statistically defensible target enrollment given the high fluoride varnish application frequency in our study and the ~ 2.5 years of follow-up time from birth. Moreover, genuine treatment effects occurring below our statistical detection threshold or within highly variable decay experiences are unlikely to be clinically and ecologically relevant. Both calculations are based upon the average effects of fluoride varnish alone⁹ and thus should be conservative. In this regard an Australian trial that enrolled expectant Aboriginal women suggests the combination of MI and fluoride varnish results in a larger treatment effect than varnish alone³ and that this difference persisted over 5 years of follow up.¹⁵ Power analysis based upon their data is presented in the section below.

On average 9 and 23 women per month give birth at Hopi and Crow, respectively. We target recruiting 7 per month at Hopi and 18 per month at Crow. This will achieve our target enrollment by 14 months and will accrue a larger number of participants at Crow (N=252) than Hopi (N=98). Our study is not designed to compare intervention effectiveness across tribes but rather across treatment groups. Therefore, the enrollment imbalance across sites does not affect our primary research question as both groups will be combined when evaluating all outcomes.

Secondary outcome power analysis

Secondary outcomes include a complementary caries measure and a set of caregiver-assessed health knowledge and behavior domains.

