12.4 Final Analysis Plan

Descriptive analyses will include calculating means and proportions and their associated measures of variability. We will also compare key sociodemographic differences across those who do and do not complete the study (attrition analysis). As per CONSORT guidelines¹⁷ we will not statistically compare participant baseline characteristics across treatment arms.

Missing data. We will multiply impute missing values for the primary outcome for all participants enrolled and randomly assigned to a treatment (intention to treat). We will impute within each treatment group¹⁸ based upon key sociodemographic factors (maternal age and education; tribe; child sex) assuming the data are missing at random. Multiply imputed estimates of regression coefficients and standard errors will be combined using Rubin's rules. The primary outcome is a continuous variable.

The focal intention to treat analysis of the intervention will be evaluated by regressing dmfs at follow up on a binary treatment group variable using robust variance estimates. We will include child sex, child age in months at follow up and site (Hopi/Crow) as covariates. Although randomization should balance the treatment groups, age and sex are strongly associated with dmfs scores⁷ and covarying those variables should increase efficiency. Covarying child age also statistically controls for follow up length. In contrast, covarying the (log) number of tooth surfaces in analysis of childhood caries did not predict dmfs in a similar RCT.² We are not powered to compare treatment differences across site but using site as a covariate will increase sensitivity in the context of possible site differences in caries.

Robust variance estimation in OLS regression will provide more accurate variance estimates in the presence of assumptive violation, i.e., heteroscedasticity. If the model is homoscedastic robust regression will provide estimates close to non-robust OLS estimates.¹⁹ This approach obviates the need to prespecify the correct form of assumptive violation.

Analysis of the oral health secondary outcome (dmft) will parallel dmfs analyses. Other secondary outcomes involving questionnaires will regress post-test scores (Visit 6) on a binary treatment indicator variable using baseline values as a covariate.

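### Near-costless improvement, not an error: add maternal age and education, already used to impute missing dmfs, to the covariates of the primary model

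*Combined protocol and SAP*

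**What the plan says.** The plan makes three relevant statements about these variables in the combined protocol and SAP.

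- **Primary model (12.4).** dmfs at follow-up is regressed on treatment by OLS with robust variance. On covariates: "We will include child sex, child age in months at follow up and site (Hopi/Crow) as covariates". Reasons are given for each. Child age and sex are said to be related to dmfs and so to improve efficiency, age also accounts for length of follow-up, and site enters because caries levels might differ between sites. One candidate, the log number of tooth surfaces, is mentioned and set aside because it had no predictive value in a similar trial. The dmft analysis follows the same pattern.
- **Missing data (12.4).** Missing dmfs is multiply imputed within treatment group, under missing at random, from "key sociodemographic factors (maternal age and education; tribe; child sex"). Section 12.1 adds the 12-month dental assessment as an imputation predictor.
- **Collection (7.1).** "A small subset of demographic questions (~20 items) will be assessed at the consent visit". The items are not listed there.

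On power, the calculation in 12.2 is set up "with power = 0.80, alpha = 0.05 (two tailed"). It compares two unadjusted group means by t-test, and its result under the main SD is that "a sample of 352 is necessary to detect a 37% reduction in caries experience (dmfs of 14 vs 8.8; SD=17.25"). It then says "With 19% attrition we would retain an effective sample size of 283.5", and continues: "conservative we round down to an even number of 282 (141 per group) which provides power of 0.71 for a 2-tailed test". A second scenario uses a smaller spread: "A 35% reduction in the standard deviation (SD=11.2) for the same effect size would require only 150 participants". With that SD the stated power at 282 is 0.97.

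**The concern.** Tribe (as site) and child sex appear in both the imputation list and the adjustment list. The two maternal variables appear only in the first, and 12.4 does not say why. They are fixed before treatment starts, so adjusting for them raises none of the difficulty that adjusting for the 12-month dmfs would.

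The plan's own reason for adjusting is efficiency, and it admits site on no more than a possible difference in caries. By that standard maternal age and education are reasonable candidates. Their use in imputation also suggests that the planners expect some link to dmfs, because a variable related only to dropout, and not to dmfs, removes no bias from imputed dmfs values.

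What is at stake is precision. The plan accepts power of 0.71 under its main SD. It acknowledges in 12.2 that varnish in the comparison arm may shrink the difference. Recruitment is tied to local birth numbers, and 5.3 rules out replacing lost participants. Covariate adjustment is one of the few ways left to gain precision without more families.

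**Working it through.** **Inputs from 12.2.** Means 14 and 8.8, so the difference is 5.2 as rounded (37% of 14 is 5.18). SD 17.25. Two-sided alpha 0.05. Retained N = 350 × 0.81 = 283.5, rounded down to 282, or 141 per arm.

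**Step 1: reproduce the plan's figure.** For an unadjusted two-sample t-test the noncentrality is δ / (SD × √(2/n)).

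- δ = 5.18: 5.18 / (17.25 × √(2/141)) = 5.18 / 2.054 = 2.52, giving power 0.710.
- δ = 5.2: 5.2 / 2.054 = 2.53, giving power 0.713.

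The stated 0.71 reproduces. So does the 352 for power 0.80 (exactly, with δ = 5.18), and the 0.97 with SD 11.2.

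**Step 2: add covariates.** If the two variables explain a share R² of the residual variance of dmfs, then:

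- residual SD = 17.25 × √(1 − R²)
- standard error is multiplied by √(1 − R²)
- equivalent extra completers = 282 / (1 − R²) − 282

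The documents give no R², so every value below is an assumption. The power range covers δ = 5.18 to 5.2.

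| Assumed partial R² | Residual SD | Power | CI narrower by | Equivalent extra completers |
|---|---|---|---|---|
| 0% | 17.25 | 0.710–0.713 | 0% | 0 |
| 1% | 17.16 | 0.714–0.717 | 0.5% | 3 |
| 2% | 17.08 | 0.718–0.722 | 1.0% | 6 |
| 5% | 16.81 | 0.732–0.735 | 2.5% | 15 |
| 10% | 16.36 | 0.754–0.758 | 5.1% | 31 |

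**Step 3: cost in degrees of freedom.** With δ = 5.2 and R² = 0, removing 2 degrees of freedom leaves power at 0.7131 and removing 5 leaves it at 0.7130. The cost is below 0.001.

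**Step 4: what would reach 0.80.** From the unadjusted start with δ = 5.2, R² would have to be about 0.19. Two maternal demographics should not be counted on for that.

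**Step 5: allow for the covariates already planned.** The 0.71 ignores child sex, child age and site. If those three explained 10% of the variance (assumed), the planned model would have power of about 0.758 with δ = 5.2. A further 1% or 5% partial R² would then give 0.762 or 0.779. The increment is of similar size, but the starting point is higher.

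**The case against.** The strongest reply is that nothing in the plan is wrong, and most of it stands.

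- A reader might infer that the plan contradicts itself by treating these variables as predictors of dmfs in one place and ignoring them in another. The documents do not support that. They nowhere say that maternal age or education predicts dmfs. Variables may be put in an imputation model because they relate to missingness, and an imputation model richer than the analysis model is accepted practice. The use in imputation points to an expected link with dmfs, but does not establish one.
- A reader might infer that omitting them biases the result or leaves chance imbalance as a flaw. Randomisation keeps the planned estimate unbiased, and chance imbalance is already reflected in its standard error.
- A reader might infer that the shortfall from 0.80 to 0.71 is the price of omission. It is not. The 0.71 is an unadjusted t-test figure that precedes any covariate, and under the smaller SD the plan already states 0.97, where little is left to gain.
- The authors gave reasons, partly from cited studies, for the covariates they chose, and none is offered for these two. That is fair, but site was admitted on a possible difference only, so the plan does not itself demand proof of association.
- The change is not wholly free. Section 7.1 does not name education among its items, 12.4 describes imputation for the primary outcome only, and education needs a coding. A missing maternal value could otherwise drop a randomised dyad. This stands, and the fix has to cover it.

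**Conclusion.** This is an optional improvement in efficiency, not an error. Maternal age and education are plausibly prognostic baseline factors that the plan already needs for imputation, and adjusting for them fits its stated reason for using covariates. The likely gain is small: about 0.4 to 2.2 points of power if they explain 1% to 5% of the remaining variance, about 4.5 points at 10%, and nothing if they do not predict dmfs.

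Those figures assume the plan's main SD of 17.25, 141 completers per arm and the full 37% reduction, and R² values that the documents do not supply. They do not show that the trial is losing material power, nor that 0.80 is within reach this way. The case rests on a possible modest gain set against a cost below 0.001 in power.

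**What to change.** Before any outcome data are seen, state in 12.4 that the dmfs and dmft models adjust for:

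- site, child sex and child age at follow-up, as now; and
- maternal age and maternal education as recorded at enrolment for the randomised mother. These values are kept if another caregiver takes over under 5.5.2.

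In the same place, fix the coding of education (categories, or a linear score) and say that any missing value of maternal age or education is imputed in the same multiple-imputation model as dmfs, so that no randomised dyad drops out of the analysis. Confirm that education is among the items asked at the consent visit.

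The cost is a few degrees of freedom and a short edit to 12.4, including one extra sentence on missing covariates. If the two variables are collected as the imputation plan requires, no new data, participants or visits are needed. If the sponsor prefers the shorter covariate list, one sentence giving the reason would be enough.

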Précis: Early Childhood Caries (ECC) is the most common chronic disease among children. American Indian (AI) children are 4 times more likely to have untreated dental decay than white children. This is a four year parallel group randomized clinical trial evaluating the impact of a bundled best practices oral health intervention on early childhood caries in American Indian children as indicated by the number of decayed, missing and/or filled primary tooth surfaces (dmfs). The intervention is delivered during pregnancy and through child age 24-36 months. The bundled best practices include motivational interviewing with mothers and fluoride varnish applied to the child's teeth. The oral health intervention also includes Tribe-specific individual, social and health needs identified in an earlier formative assessment. The oral health intervention group (n=175 mother-child dyads) will be compared to a group (n=175 mother-child dyads) receiving a standard prenatal/postnatal healthy lifestyle intervention. All study treatments will be delivered by Community Health Representatives in the Hopi (Arizona) and Crow (Montana) communities. Children will be followed until 2 - 3 years of age.

Objectives:	
Primary Objective: To determine whether children in the OH group compared to the Healthy Lifestyle group have on average fewer decayed, missing and/or filled primary tooth surfaces (dmfs) measured at the last visit.
 
Secondary Objective 1: To determine whether children in the OH group compared to the Healthy Lifestyle group have on average fewer decayed missing or filled teeth (dmft) measured at the last visit.
 
Secondary Objectives 2-4: To examine if women in the OH group compared to the Healthy Lifestyle group have greater increases in:
 
• Oral health knowledge• Oral health behavior• Positive attitudes towards oral health care 
These will be compared as changes from baseline (Visit 1) to the last (Visit 6) survey assessment.
 
Secondary Objective 5: To examine if women in the Healthy Lifestyle group compared to the OH group have greater increases in knowledge of developmental milestones, pregnancy related nutrition, breastfeeding and prenatal health at Visit 6 relative to baseline (Visit 1).

Population:	Healthy pregnant women who are American Indian (AI) or giving birth to an AI child on or near the Hopi and Crow Nations in Arizona and Montana, respectively, and their infants, once born.

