To determine whether mothers/caregivers in the OH group compared to the Healthy Lifestyle group perform more of the optimal care practices for their child's teeth (oral health behavior)	Optimal oral health care is reflected in the oral health behavior survey items (e.g., regular checking of teeth/gums; use of fluoride toothpaste; avoiding sugary food and drink; caregiver brushing frequency). These care behaviors are inversely correlated with childhood dmfs scores ⁷ and may reflect a treatment pathway.	We will assess oral health behavior with a 16-item assessment adapted from the BRFQ and prior studies of AI infants/children. Responses will be scored as the percent of responses with "adherent" or optimal oral health behavior.	This outcome is measured after the child is 12 months of age (Visit 4), 18 months of age (Visit 5) and again at child age 24 months (Visit 6).
To determine whether mothers/caregivers in the OH group compared to the Healthy Lifestyle group show more favorable attitudes towards oral health care	Attitudes towards desirable oral health behavior should change following the intervention and may track with intervention efficacy.	Attitudes are measured using 14 items that parallel the behavior questions (e.g., How important is it to you to check teeth/gums every month?). A sum of Likert-style ratings will comprise the attitudes. These items are labeled "motivation" in the BRFQ instrument.	This outcome is measured at baseline (Visit 1; while expecting), after the child is 12 months of age (Visit 4) and again at child age 24 months (Visit 6).
To determine whether mothers/caregivers in the Healthy Lifestyle group compared to the OH group show increases in maternal/child health knowledge (non-oral health)	Maternal/child health knowledge is a target of the comparison group treatment and will be assessed to compare this knowledge across the two study groups.	We will assess maternal/child health knowledge with a 20-item assessment. Source items come from the Healthy Lifestyle modules and will be scored as a percent correct, excluding the filler items.	This outcome is measured at baseline (Visit 1; while expecting), after the child is 12 months of age (Visit 4) and each visit until the child is 24 months (Visits 5 & 6).

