The healthy lifestyle intervention will provide education and support for mothers regarding pregnancy, postpartum challenges, food preparation for children 12 months and older, infant nutrition, and parenting. This also includes a short module on oral health. The intervention will be administered by trained CHRs. Six sessions are scheduled for the healthy lifestyle group, with timing parallel to the timing of sessions in the oral health arm. Children in this arm will receive a fluoride varnish application by study staff at 12 months and 24 months. Children in the HL arm in the early cohort will receive a third FV application after their final study visit at child age 30-36 months.

Children in both groups will be scheduled for a full oral health assessment at 12 (Visit 4) and 24-27 months (Visit 6). Earlier recruits (through month 8 recruitment) will be followed up longer for a final oral assessment (Visit 7 at 30-36 months of age).

Assessments will be conducted by calibrated dentists and/or hygienists, masked to the study condition. Mothers will be reminded of their appointments through follow-up phone calls and/or in person visits from the Community Health Representatives. Dentists will provide oral assessment data to study staff who will securely upload the data into REDCap and securely store the records.

Secondary outcomes of oral health knowledge, behaviors, and attitudes and knowledge of maternal and child health issues not related to oral health will be assessed using questionnaires. Oral health knowledge and maternal child health knowledge will be assessed at Visits 1, 4, 5 and 6. Oral health attitudes will be assessed at Visits 1, 4 and 6 and oral health behavior will be assessed at Visits 4, 5 and 6. Survey data will be securely collected via laptop or tablet using REDCap software.

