7.2 Visit 1 Overview/Baseline

Baseline data will be collected on the mothers/caregivers, including oral health knowledge and attitudes; social support, insurance and health care utilization. Mothers/caregivers in the OH group will receive the first MI intervention module. Mothers in the HL group will receive the first Healthy Lifestyle intervention module.

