7.3 Study Visit Descriptions

7.3.1 *Visit 1 (3-7 months pregnant; 9-31 weeks pregnant)*

The range of months is broad because of the potential difficulty of enrolling expectant mothers at a precise gestational epoch. We will make every effort to recruit women shortly after the first trimester but to facilitate enrollment women through 7 months of pregnancy are eligible which will still permit a second intervention session at least 30 days after the first session and prior to giving birth.

- Obtain sociodemographic assessments; oral health knowledge and attitudes; oral health self-efficacy; maternal and child health knowledge.
- Administer the OH or HL intervention.

7.3.2 *Visit 2 (7-9 months pregnant; 28-40 weeks)*

- Visit 2 must occur at least 30 days after visit 1.
- Administer the OH or HL intervention.
- Assess social determinants such as transportation, health literacy, dentist trust, social relationship resources.
- Record participant's compliance with OH or HL intervention.
- Record adverse events as reported by participant or observed by investigator.

7.3.3 *Visit 3 (Child 6 months of age ± 1 month)*

- Assess child demographics, insurance and transportation; social determinants; communication, trust and satisfaction with CHR.
- Administer the OH or HL intervention.
- Administer fluoride varnish to any erupted teeth among OH arm children.
- Record participant's compliance with OH or HL intervention.
- Record adverse events as reported by participant or observed by investigator.

7.3.4 *Visit 4 (Child 12 months of age ± 1 month)*

- Visit 4 may take place over two days. The child's oral health assessment and FV application will always go first (i.e., on Day 1) and the OH/HL intervention will follow (on Day 2). These may be completed on the same day as long as the oral assessment and FV application happen first.
- Child oral health assessment for both OH and HL arms.
- Administer fluoride varnish to erupted teeth among OH and HL arm children.

- Assess oral health knowledge, behavior and attitudes; maternal/child health knowledge; social determinants; dental self-efficacy, trust and satisfaction with CHR; social support.
- Administer the OH or HL intervention.
- Record participant's compliance with OH or HL intervention.
- Record adverse events as reported by participant or observed by investigator.

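### The baseline covariate in Section 12.4 and the Visit 1 to Visit 6 change in the Protocol Summary do not exist for oral health behavior, which is first measured at Visit 4

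*Combined protocol and SAP*

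**What the plan says.** **Analysis model.** Section 12.4: "Other secondary outcomes involving questionnaires will regress post-test scores (Visit 6) on a binary treatment indicator variable using baseline values as a covariate". No questionnaire outcome is exempted, and site is not in this model. The dmfs model in the same section does include site.

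**Objective in the Protocol Summary.** Secondary Objectives 2-4 are oral health knowledge, behavior and attitudes. Of these the summary says: "These will be compared as changes from baseline (Visit 1) to the last (Visit 6) survey assessment".

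**Objective and hypothesis elsewhere.** Section 3.2 asks whether mothers or caregivers in the oral health group "perform more of the optimal care practices" than those in the other group. Section 12.1 sets the behavior hypothesis as equality of the two group means at Visit 6.

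**When behavior is measured.** Section 3.2: "This outcome is measured after the child is 12 months of age (Visit 4), 18 months of age (Visit 5"), and then again at Visit 6. Section 4 agrees: "oral health behavior will be assessed at Visits 4, 5 and 6".

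**What is collected at Visit 1.** Section 7.2: "Baseline data will be collected on the mothers/caregivers, including oral health knowledge and attitudes; social support, insurance and health care utilization". Section 7.3.1: "Obtain sociodemographic assessments; oral health knowledge and attitudes; oral health self-efficacy; maternal and child health knowledge". Behavior is in neither list. The first visit list to name it is that for Visit 4, in Section 7.3.4.

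**The concern.** The model in Section 12.4 and the comparison in the summary both need a Visit 1 behavior score, and the schedule never collects one. The gap is structural: the behavior items concern care of the child's teeth, and at Visit 1 the study child is not yet born.

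The analyst will therefore have to depart from Section 12.4 for this outcome, and the plan does not say how. At least three substitutes are open: no baseline term, a proxy covariate from Visit 1, or the earliest behavior score available. The last would be a poor choice, because that score follows randomization and several intervention sessions. The model should be fixed before the data are seen. Section 3.2 also describes behavior as a possible treatment pathway, and the end of Section 12.4 lists it as a candidate mediator.

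A smaller and separate matter is that allocation is blocked by site (Section 5.4.1), yet the questionnaire models leave site out.

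**Working it through.** **Step 1. Does each questionnaire outcome have a Visit 1 value?** (Sections 3.2 and 4)

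| Outcome | Visits measured | Visit 1 value? |
|---|---|---|
| Oral health knowledge | 1, 4, 5, 6 | yes |
| Oral health attitudes | 1, 4, 6 | yes |
| Maternal/child health knowledge | 1, 4, 5, 6 | yes |
| Oral health behavior | 4, 5, 6 | **no** |

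The first three models can be run as written; the behavior model cannot. The prose sections establish this without Appendix A, whose table is damaged in the text available.

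**Step 2. Could a later score count as the baseline?** The summary defines baseline as Visit 1, and Section 7.2 has Visit 1 and baseline in one heading. Section 4 schedules two sessions before birth and one at 6 months, so three sessions precede Visit 4 at 12 months. Adjusting for a Visit 4 or 5 score, or taking change from it, could remove part of the treatment effect.

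**Step 3. What can be detected with no baseline covariate?** The plan gives no power figure for behavior, so there is none to reproduce. Inputs: 141 per arm (Section 12.2); two-sided alpha 0.05 and 80% power (assumed for this outcome).

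Detectable difference = (1.960 + 0.842) × √(2/141) = 2.802 × 0.1191 = 0.33 SD.

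**Step 4. What does leaving out site cost for behavior?** Inputs: planned enrollment of 252 at Crow and 98 at Hopi (Section 12.2), so q = 98/350 = 0.28. The site difference s, in within-site SDs, is not in the documents; I assume 0, 0.5 and 1.0.

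- Variance added by site: v = q(1 − q)s² = 0.2016 s².
- Ratio of the reported standard error without site to that with site: √(1 + v).
- With arms balanced within site, the arm estimate and its true sampling variance do not depend on whether site is in the model. Only the reported standard error grows. An effect with 80% power therefore has power Φ(2.802 − 1.960 × √(1 + v)) without site.

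| s (assumed) | v | SE ratio | Power without site |
|---|---|---|---|
| 0 | 0 | 1.000 | 0.80 |
| 0.5 | 0.0504 | 1.025 | Φ(2.802 − 2.009) = 0.79 |
| 1.0 | 0.2016 | 1.096 | Φ(2.802 − 2.149) = 0.74 |

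A simulation of 20,000 trials for each s (282 participants split 202/80 by site, arms balanced within site, true difference 0.335 SD) gave the same rounded powers of 0.80, 0.78 to 0.79 and 0.74. The arm estimates with and without site were identical.

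**Step 5. The three baseline-adjusted outcomes.** Assume the same s at Visits 1 and 6 and a within-site correlation r. The ratio is √{[(1 + v) − (r + v)²/(1 + v)]/(1 − r²)}. At r = 0.5 it is 1.008 for s = 0.5 and 1.028 for s = 1.0. The baseline score already absorbs most of the site difference.

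**The case against.** **The behavior question is still answerable.** A reader might infer that the behavior objective cannot be evaluated at all. The documents do not support that. Section 3.2 compares the arms on care practices, without asking for an increase, and Section 12.1 compares Visit 6 means. Both can be computed. Only the summary wording and the covariate in Section 12.4 fail. This part of the objection stands and limits the point to a specification gap.

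**Section 12.1 already settles the analysis.** Only in part. It states the contrast; Section 12.4 states the model. An analyst following 12.4 still finds a required term missing.

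**The plan might be read as intending Visit 4 as the baseline.** Nothing in it proposes this. The sentence suggested below only closes off the option.

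**Attitudes at Visit 1 could stand in.** Section 3.2 says "Attitudes are measured using 14 items that parallel the behavior questions", so this is reasonable. But at an assumed correlation of 0.3 the detectable difference moves only from 0.334 to 0.334 × √(1 − 0.09) = 0.318 SD, and leaving the covariate optional would reopen the choice that needs closing.

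**Site is a preference, not an error.** This stands. The plan nowhere promises site adjustment for questionnaires, its reason for using site concerns caries, and the documents give no site difference in any survey score. A reader might infer bias from the omission; there is none. A reader might also divide the standardized effect by the standard error ratio and get power of 78% and 72%. That treats the estimate's true variance as inflated, which it is not when arms are balanced within site.

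**Conclusion.** The mismatch is certain from the text: for oral health behavior, the Section 12.4 covariate and the summary's change score both rely on a Visit 1 measurement that is not made. It affects one of five secondary outcomes. The primary analysis, dmft and the other three questionnaire models can proceed as far as this point is concerned, and no result is biased by it. It should be fixed because a stated analysis cannot be run as written and its replacement is left open.

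Adding site is a precision improvement, not a correction. For behavior, omitting it leaves the reported standard error unchanged if the sites do not differ, and makes it about 2.5% or 9.6% too large if they differ by 0.5 or 1.0 within-site SD. Power of 80% is then unchanged, or about 79% or 74%. These figures rest on the assumed site differences, the planned 252/98 split and arms balanced within site. The gain is nil if the sites are alike.

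**What to change.** 1. **Section 12.4:** exempt oral health behavior from the baseline covariate and name one model: the Visit 6 behavior score regressed on arm and site, with no baseline score.
2. **Section 12.4:** state that Visit 4 or Visit 5 behavior scores will not serve as a baseline, because they follow randomization and intervention sessions.
3. **Protocol Summary:** take behavior out of the change-from-baseline wording and state its objective as the Visit 6 difference between arms, as in Section 12.1.
4. **Separately, for precision only:** add site, the randomization stratum, to all questionnaire models.

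The cost is a few sentences in the summary and Section 12.4. No new data, visits or participants are needed.
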